9.3 Safety analyses

9.3.1 Adverse Events

AEs will be summarized presenting the number of events, the number of subjects and percentage. When calculating the incidence of AEs, or by seriousness sub-classification, each subject will only be counted once and any repetitions of AEs will be ignored; the denominator will be the total population size. In case of repetition of an AE the worse seriousness will be considered.

An overview table (Shell T-5) will be prepared showing the number of subjects (percentage of subjects, and events) with:

- Adverse Events
- Adverse Events by relationship to SNF472
- Adverse Events leading to drug discontinuation
- Serious Adverse Events
- Adverse Events leading to death

In addition, frequency tables (Shell T-5) will be prepared for:

- Adverse Events by System Organ Class and Preferred Term
- Adverse Events by Preferred Term in Decreasing Order of Incidence
- Adverse Events by System Organ Class and CTCAE Grade
- Adverse Events by System Organ Class and Relationship to SNF472
- Adverse Events Leading to Discontinuation of SNF472 by System Organ Class
- Serious Adverse Events by System Organ Class and Preferred Term

9.3.2 Clinical Laboratory Evaluations

Summary tables will be presented in groups of related parameters:

- Haematology
- Clinical Chemistry
- Parathyroid Hormone
- Potassium, magnesium, iron (ferritin/transferrin) and zinc
- Ionised Calcium
- Pregnancy test

Analyses are conducted for the laboratory data using SI units.

Haematology and **Clinical chemistry** data will be collected at Screening, Week 1, Week 6, Week 12 and Follow-up. Absolute change from baseline values for each parameter will be summarized descriptively. (Shell T-7).

Parathyroid Hormone data will be collected at Week 1 and Week 12. Absolute change from baseline values for each parameter will be summarized descriptively. (Shell T-7).

Potassium, magnesium, iron (ferritin/transferrin) and zinc data will be collected at Screening, Week 1 (pre and post-dose), Week 12 (pre and post-dose) and Follow-up. Differences in absolute change from the pre-dose measurement of each visit to the post-dose measurement of the same visit, and the differences in absolute change from Baseline to all measures will be summarized (Shell T-7).

Ionised Calcium data will be collected at Screening, Weeks 1, 2, 4, 6, 8, 10 and 12 (pre and post-dose), and Follow-up. Differences in absolute change from the pre-dose measurement of each visit to the post-dose measurement of the same visit, and the differences in absolute change from Baseline to all measures will be summarized (Shell T-7).

Pregnancy test data will be collected at Screening, Week 1, Week 4, Week 8 and Week 12. The following variables will be summarized: Done/ not done, if any, reason for not done. Sample type and results by visit (Shell T-6).

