## 2.3. Risk-Benefit Assessment

The currently available information of clinical experience with IV IP6 is based on:

1. Technetium formulations for bone and other scans
2. A single ascending dose study of SNF472 in healthy volunteers
3. Both a single and repeated ascending dose study in haemodialysis patients treated for up to 28 days

SNF472 has been extensively studied in non-clinical models for efficacy, safety, pharmacokinetics, and toxicity. The main toxicological finding with SNF472 in animals – at high doses only - is hypocalcaemia due to chelation of ionised

calcium. The symptoms and signs observed include ECG effects, particularly transitory and reversible QTc prolongation. This is seen at  $C_{max}$  values about 100-fold higher than the expected therapeutic levels. The effect is not present in animals when the same bolus doses are administered by slow intravenous infusion. Moreover, SNF472 does not block the hERG channel (Study No SNFSF2010\_01 A0189 [43]). The hypocalcaemia and the associated QTc effect are rapidly reversed by intravenous calcium gluconate. It is expected that the risk of associated hypocalcaemia will be minimal in haemodialysis patients, as slow infusions ranging from 2.5 to 4 hours will be used and the plasma calcium concentration is controlled by the calcium content of the dialysis fluid. Furthermore, in the unlikely situation of hypocalcaemia symptoms and signs occurring, they can be reversed by the administration of IV calcium-gluconate.

During the phase I studies with volunteers, single doses from 0.5 mg/kg to 12.5 mg/kg were administered (SNFCT2012\_03 Part C). A single dose of 9 mg/kg (SNFCT2012\_03 Part C) and repeated doses from one to 20 mg/kg were studied (SNFCT2014\_03) in haemodialysis patients. In healthy volunteers, SNF472 was generally well tolerated, except for the occurrence of mild to moderate local infusion site irritation. Infusion site irritation is not an issue in HD patients, as SNF472 is injected into the HD tubing and passes through a volume of blood of at least 200 mL before reaching the patient's blood vessels.

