Baseline values are a (placebo pre-dose and at 12 hours, b (active treatment pre-dose) and c (active treatment at 12 hours). (mmol/L). Green line: Normal range:1.17-1.30 mmol/L. Red line: 0.5 mmol/L: possibility of tetany and potentially life-threatening

The planned doses in the protocol were 0.5, 1.5, 5, and 10 mg/kg. PK simulation based on preclinical data predicted plasma concentrations ( $C_{max}$ ; ng/mL) of 3000, 10000, 30000 and 70000 respectively. After the 1st cohort (0.5 mg/kg), the DESC (Dose Escalation Safety Committee) decided to increase the dose to be tested in the 2nd cohort (1.5 mg/kg) to 5 mg/kg. This decision was based on PK results showing much lower values than the anticipated systemic exposure of around 2500 ng/mL as predicted by the PK model (levels were below the limit of quantification of 500 ng/mL). According to new PK estimations, 5 mg/kg was expected to produce the initially expected level of exposure with 1.5 mg/kg. The  $C_{max}$  with 5 mg/kg was 11571 ng/ml, which is nearly triple the anticipated EC50. Using the PK data of the 5 mg/kg dose and the safety data after each cohort, the DESC decided to modify the following two doses to reach the target concentrations. The doses of 9 and 12.5 mg/kg produced SNF472 plasma levels of 24394 and 42207 ng/mL, respectively.

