9.1.7 Treatment exposure and compliance

The extent of exposure to SNF472 will be characterised according to the number of subjects exposed, the duration of exposure, and the dose to which they were exposed.

The following data will be summarized descriptively for the total treatment period and by week (Shell T-6):

- **Treatment duration (days)** defined as the total number of days between the first and the last infusion dates (inclusive).

-
- **Treatment exposure (infusions)** defined as the number of infusions with the study drug of at least 1 hour that were administered to a subject.
 - **Compliance (%)** defined as the total number of infusions administered to a subject divided by the total number of planned infusions, i.e, 3 administrations x 12 weeks of treatment = 36.
 - **Dose (mg)** presented as a categorical variable indicating the number and percentage of subjects presented on the different planned dose levels (400, 450, 700, and 900 mg).
 - **Total dose (mg) (an estimation of the total dose)**
 - **Dialysis duration (minutes)** defined as the time in minutes registered between the start of the dialysis start and it end.
 - **Infusion duration (minutes)** defined as the time in minutes registered between the start of the infusion and its end.
 - **Number of infusions with any interruptions** counting the number of infusions per subject where the question "Infusion interruptions" is Yes.
 - **Ca in Dialysate Bath** presented as a categorical variable.

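### SAP 9.3.2 specifies change summaries for ionised calcium but no count of low values and no shift table, so its tables would not show how many patients ended infusion below normal

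*SAP*

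**What the plan says.** **Hazard.** Protocol 2.3 reports that the main toxicological finding in animals, "at high doses only - is hypocalcaemia due to chelation of ionised" calcium. It adds a reassurance for this trial: "It is expected that the risk of associated hypocalcaemia will be minimal in haemodialysis patients".

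**Data.** SAP 9.3.2 states: "Ionised Calcium data will be collected at Screening, Weeks 1, 2, 4, 6, 8, 10 and 12 (pre and post-dose), and Follow-up".

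**Planned summaries.** SAP 9.3.2 gives two for ionised calcium: "Differences in absolute change from the pre-dose measurement of each visit to the post-dose measurement of the same visit", and the change from Baseline to every measurement. Both refer to Shell T-7. The section mentions no lower limit, no count of falls beyond a set size and no shift table.

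**Comparison within the SAP.** For QTc, SAP 9.3.3 plans change summaries and also counts of subjects above 450, 480 and 500 ms and with increases above 30 and 60 ms, at any time and by visit. It plans shift tables for the ECG clinical assessment.

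**General rules.** Protocol 9.2 covers safety parameters and asks for n, mean, SD, median, minimum and maximum. SAP 8.9.2 fixes only N, mean and SD for continuous variables and leaves the range to be used where appropriate. SAP 8.1 lists all recorded data by subject.

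**Reference range.** The note to Protocol Figure 1 gives "Normal range:1.17-1.30 mmol/L".

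**The concern.** Whether calcium fell too low is a question about individual patients and about the level reached. A summary of change answers a different question, namely how far values moved on average. A few marked falls can be offset by small rises in the others. Even without offsetting, the size of a change does not say on which side of the normal limit the patient finished.

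The protocol's expectation of minimal risk is a premise that this trial could test. Protocol 2.3 rests it partly on limited data in dialysis patients. Protocol 2.3.2 says that most ionised calcium samples from the healthy-volunteer study could not be analysed, and that the sparse remainder suggested a possible dose-related decrease. Earlier repeated dosing lasted up to 28 days, whereas this trial doses for 12 weeks. If the tables show only mean changes near zero, the report could state that there was no effect on calcium without saying how many patients were low at the end of infusion.

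**Working it through.** The plan states no figure on this point, so there is none to reproduce. The check compares what each planned output can show and illustrates it with assumed changes.

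**Inputs from the documents.** Up to 15 subjects (SAP 6.1). Pre-dose and post-dose ionised calcium at seven treatment weeks plus Screening and Follow-up (SAP 9.3.2), which is 1 + 7 × 2 + 1 = 16 values per patient and up to 15 × 7 = 105 pairs. Normal range 1.17 to 1.30 mmol/L (Protocol 2.3.2, Figure 1 note), a width of 1.30 − 1.17 = 0.13.

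**Assumed inputs.** All individual changes below. The documents give no ionised calcium results for this trial.

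**Step 1: can summaries of change conceal a few falls?**

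| Assumed changes, N = 15 (mmol/L) | Mean | Median | SD | Minimum |
|---|---|---|---|---|
| 2 fall by 0.30, 13 rise by 0.05 | (−0.60 + 0.65)/15 = +0.003 | +0.05 | 0.123 | −0.30 |
| 3 fall by 0.20, 12 rise by 0.05 | (−0.60 + 0.60)/15 = 0.000 | +0.05 | 0.104 | −0.20 |
| 1 falls by 0.30, 14 rise by 0.03 | (−0.30 + 0.42)/15 = +0.008 | +0.03 | 0.085 | −0.30 |

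The mean and median show nothing. The minimum shows the largest fall each time, but not whether one, two or three patients had it.

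**Step 2: does change determine who ended below normal?** It does not.

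- A fall of 0.13 from 1.30 ends at 1.17, which is on the limit. The same fall from 1.17 ends at 1.04, which is below it.
- A fall of 0.15 ends at 1.15 from 1.30, but at 1.02 from 1.17.
- A rise of 0.05 from 1.02 ends at 1.07, still below normal.

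Take the first row of the table. If all 15 patients start within the range, the two who fall end between 1.17 − 0.30 = 0.87 and 1.30 − 0.30 = 1.00, and nobody else is below 1.17, so the count is 2. Any of the other 13 who started below 1.17 − 0.05 = 1.12 would also end below normal. The same change table therefore fits very different counts.

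**Step 3: do other planned outputs supply the count?**

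- QTc counts: treatment-period ECGs are at Weeks 1, 6 and 12 (SAP 9.3.3), against seven weeks for ionised calcium. Protocol Table 1 limits ECGs to sites with suitable equipment and trained staff.
- Adverse events: under Protocol 7.1.2.2, an abnormal value becomes an adverse event only if the investigator judges it clinically significant.
- Listings: they contain the values, but a reader would have to derive the count.

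**Step 4: what would the count deliver at this size?** Exact two-sided 95% intervals for the any-visit count with N = 15:

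| Subjects below limit | Percentage | 95% CI |
|---|---|---|
| 0 | 0% | up to 21.8% |
| 1 | 6.7% | 0.2% to 31.9% |
| 2 | 13.3% | 1.7% to 40.5% |
| 3 | 20.0% | 4.3% to 48.1% |

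The count would be imprecise, but it addresses the question directly.

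**The case against.** A reader might infer more than the documents support, in four ways.

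- **That marked falls would be hidden.** They would not. Protocol 9.2 calls for the minimum and maximum, and SAP 8.1 lists every value by subject for at most 15 patients. SAP 8.9.2 does not itself guarantee the range, but it does not withdraw the protocol's rule either.
- **That observed values will not be tabulated at all.** This cannot be settled. Shell T-7 is not in the available text, and SAP 9.2.2.3 cites the same shell for VAS, where scores by visit are summarised as well as changes. The protocol synopsis also says safety parameters are summarised by time-point. If T-7 includes observed values with a minimum, the lowest end-of-infusion value will be visible, though still not the number of patients below the limit.
- **That hypocalcaemia is SNF472's main toxicity in these patients.** Protocol 2.3 confines the finding to animals at high doses and expects minimal risk in haemodialysis. Protocol 2.3.2 reports no significant decreases in ionised calcium in dialysis patients.
- **That patients are unprotected, or that the SAP contradicts itself.** Abnormalities needing corrective treatment or interruption of study drug are recorded as adverse events, and an independent medical monitor reviews safety after 5 and 10 completers and at the end (Protocol 7.1.2.8). SAP 9.3.3 attributes the QTc counts to ICH E14, and the documents cite no equivalent guidance for calcium. The QTc plan is therefore a useful model, not proof of inconsistency.

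What stands of the objection is that the information will exist in the data and listings, and that individual safety does not depend on the mean change. It does not supply a pre-specified count of low values.

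**Conclusion.** The point holds as a gap in the specified safety tables. SAP 9.3.2 names only change summaries for ionised calcium, and no change statistic can show how many patients ended infusion below normal. The gap is modest, because the largest falls can be found from the minimum and the listings. It is still worth closing, since the count bears directly on the protocol's own expectation of minimal risk.

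The size shown is illustrative. It rests on assumed changes and on a range quoted from an earlier healthy-volunteer study, whereas this trial uses local laboratories in the EU and a central one in the USA (Protocol 7.1.3). The conclusion also takes SAP 9.3.2 at its word, since Shell T-7 could not be checked.

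**What to change.** In SAP 9.3.2, keep both change summaries for ionised calcium and add:

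1. The number and percentage of subjects whose end-of-infusion value is below the reporting laboratory's own lower limit, by visit and at any visit. The denominator is subjects with an end-of-infusion value at that visit, or at least one such value for the any-visit row.
2. A pre-dose to post-dose shift table (below, within or above the normal range) at each sampled week. This separates patients who became low during infusion from those already low.
3. In the listing, dialysate calcium beside each flagged subject. SAP 9.1.7 already summarises "Ca in Dialysate Bath". With 15 patients or fewer, percentages by dialysate category would rest on very few people and add little.

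Any clinical threshold beyond the laboratory limit is for the sponsor to set. The tables can stay descriptive, in line with SAP 8.1.

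The cost is one or two small tables from data already collected, with each laboratory's reference range held in the analysis data. No visit or sample is added. Intervals will be wide, so the table should be read as a count of patients and not as a precise rate.

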9.3.3 ECG, Physical examination and Body weight

Electrocardiograms are collected at Screening, Week 1 (pre-dose and end of infusion), Week 6 (pre-dose and end of infusion), Week 12 (pre-dose and end of infusion) and Follow-up. The following variables are collected: RR interval, PRT axis, PR interval, QRS complex, QT interval, QTcB, QTcF, Heart rate and ECG Assessment, including clinical evaluation.

Differences in absolute change from the pre-dose to post-dose within the same visit, and the differences in absolute change from Week 1 day 1 pre-dose to all the following pre-dose measurements will be summarized (Shell T-7).

Following the recommendation of the guidance ICH E14, the following additional analyses on QTc for both Bazett's and Fridericia's formulas will be done:

- number of subjects with QTc interval > 450 ms
- number of subjects with QTc interval > 480 ms
- number of subjects with QTc interval > 500 ms
- number of subjects with QTc interval increases from predose > 30 ms
- number of subjects with QTc interval increases from predose > 60 ms

The previous parameters will be measured at any point during the study after the first drug infusion (Shell T-4). In addition, the same parameters will be summarized by visits Week 1 day 1, Week 6 day 1 and Week 12 day 5 for pre-dose and post-dose time-points (Shell T-6). The tables will be also presented for QT.

Shift tables on the ECG clinical assessment will be produced to present:

- Change from baseline on the pre-dose assessments to Week 6 and Week 12 (Shell T-9)
- Change from pre-dose to post-dose within infusion days at weeks 1, 6 and 12 (Shell T-10)

RR, QTcB and QTcF will be re-calculated using the following formulas, if it is possible:

$$RR = \frac{60}{HR}$$

$$\text{Bazzet: } QT_{cB} = \frac{QT}{\sqrt{RR}}$$
$$\text{Fredericia: } QT_{cF} = \frac{QT}{\sqrt[3]{RR}}$$

Physical examination was collected at Screening and Follow up Visit and it will be summarized and listed by subject, time-point and body system including the following information: parameter, assessment and clinical significance (Shell T-6).

Body weight was collected at Screening, Week 6 and Follow up Visit and it will be listed by subject and time-point including the following information: date, weight without shoes, Height without shoes and BMI.

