### **Electrocardiogram Abnormalities**

As QTc prolongation is common in ESRD patients on HD and can occur due to underlying CVC disease, haemodialysis, sodium thiosulfate, calcimimetics, electrolyte disturbances (Ca, Mg and K) and overdoses of SNF472, careful QTc assessment is essential. Any QTc interval using Bazett's formula (QTcB) >500 ms or increase >60 ms from baseline in 1 or more subjects as confirmed with consecutive ECGs will be considered abnormal. It will be reported as an AE if the investigator considers it clinically relevant. Investigators should use their discretion to monitor the subject, apply appropriate management and observe until the QTcB has decreased. At the discretion of the investigator, patients with persistent QTc prolongation may be withdrawn from the trial.

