Pain Score (VAS scale)	X	X			X						X						X						X						X																		X	X										
Lesion Score (BJWAT)		X			X						X						X						X						X																		X	X										
Biomarkers		X																																																			X					
Plasma PK and PD sampling (predose & end of infusion)*		X																																																X	X							
Concomitant Medication		X	X	X	X	X	X	X	X	X	X	X	X	X	X	X	X	X	X	X	X	X	X	X	X	X	X	X	X	X	X	X	X	X	X	X	X	X	X	X	X	X	X	X	X	X	X	X	X	X	X	X	X	X	X			
Adverse Events		X	X	X	X	X	X	X	X	X	X	X	X	X	X	X	X	X	X	X	X	X	X	X	X	X	X	X	X	X	X	X	X	X	X	X	X	X	X	X	X	X	X	X	X	X	X	X	X	X	X	X	X	X	X			
End of Study Visit																																																								X		

³ Pregnancy test is to be serum at baseline and urine monthly thereafter

⁴ Prior medication includes medications within 6 months of study start

⁵ The inclusion/exclusion criteria will be assessed for each patient at Screening – final entry into the study depends on confirmation by the PI, [name]

⁶ A Treatment Period includes 3 dialysis sessions/week x 12 weeks (36 treatments)

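### The Week 12 pre-dose ECG is taken at a different session of the dialysis week from baseline, so the Week 12 pre-dose QTc change mixes session position with SNF472 exposure

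*SAP*

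**What the plan says.** SAP 9.3.3 plans two kinds of ECG comparison.

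- **Across visits.** For the ECG intervals, "the differences in absolute change from Week 1 day 1 pre-dose to all the following pre-dose measurements will be summarized". A shift table of the clinical ECG assessment has the same basis: "Change from baseline on the pre-dose assessments to Week 6 and Week 12".
- **Within a visit.** The same section also summarises "Differences in absolute change from the pre-dose to post-dose within the same visit", with a matching within-day shift table at Weeks 1, 6 and 12.

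The session days are given in the text of 9.3.3. The QTc threshold counts are "summarized by visits Week 1 day 1, Week 6 day 1 and Week 12 day 5 for pre-dose and post-dose time-points". SAP 8.8 sets baseline at Week 1 Day 1.

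The schedule tables in both documents put sessions on Days 1, 3 and 5 of each week, and the SAP footnote reads "A Treatment Period includes 3 dialysis sessions/week x 12 weeks (36 treatments". Neither document mentions the interval since the previous dialysis session, or the position of a session within the dialysis week.

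The protocol, under Electrocardiogram Abnormalities, says that QTc prolongation "can occur due to underlying CVC disease, haemodialysis, sodium thiosulfate, calcimimetics, electrolyte disturbances (Ca, Mg and K", and adds overdoses of SNF472 to that list. Protocol 2.3.2 likewise names dialysis fluid composition and changes in Ca, Mg or K as reasons for QTc change in haemodialysis patients.

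**The concern.** A pre-dose ECG in a haemodialysis patient is read at the end of an interval without dialysis. If two pre-dose readings follow intervals of different length, their difference reflects that as well as whatever the drug has done. Here baseline and Week 6 come from the first study session of the week, and Week 12 from the third.

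This matters because the change in pre-dose values is the planned look at a sustained effect on QTc, and Week 12 is its longest-exposure point on treatment. Protocol 2.3 puts earlier repeat dosing in haemodialysis patients at up to 28 days. With a single arm, no comparison group shares the shift in session position. A reader of the Week 12 column would have no warning that it was taken under different conditions from the Week 6 column beside it.

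**Working it through.** **Inputs.** ECG days: Week 1 Day 1, Week 6 Day 1, Week 12 Day 5 (SAP 9.3.3, text). Session pattern: Days 1, 3, 5 for 12 weeks (Protocol Table 1, SAP Table 001). Column positions in the schedule tables are not used for the ECG days, because the columns are displaced in the text available for this review.

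**1. Reproduce the plan's session count.** Calendar day of Week w, Day d = 7 × (w − 1) + d. Three sessions × 12 weeks = 36, as the SAP footnote states.

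**2. Gap before each ECG session** (day of session minus day of previous session):

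- Week 6 Day 1: day 36; previous session Week 5 Day 5 = day 33; gap 36 − 33 = 3 days.
- Week 12 Day 5: day 82; previous session Week 12 Day 3 = day 80; gap 82 − 80 = 2 days.
- Week 12 Day 1: day 78; previous session Week 11 Day 5 = day 75; gap 78 − 75 = 3 days.
- Week 1 Day 1: day 1; if pre-study sessions followed the same pattern, the previous one was day −2; gap 1 − (−2) = 3 days.

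**3. Does it depend on when the patient starts?** Protocol 8.2.1 lets treatment start at any point in the two-week screening period, and nothing ties study Day 1 to the first session of the dialysis week. Take a stable thrice-weekly routine with gaps of 3, 2 and 2 days, and read Days 1, 3 and 5 as the first, second and third study session of each week:

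| Patient starts on | Gap before first study session (Weeks 1, 6, 12) | Gap before third study session (Week 12) | Week 12 v baseline as planned |
|---|---|---|---|
| 1st session of dialysis week | 3 | 2 | mismatched |
| 2nd session | 2 | 3 | mismatched, reversed |
| 3rd session | 2 | 2 | gap matched |

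**4. Why the first study session always matches.** Week 6 Day 1 is 36 − 1 = 35 days after baseline, or 5 × 7. Week 12 Day 1 is 78 − 1 = 77 days after, or 11 × 7. Whole weeks return the patient to the same point of a stable routine. Week 12 Day 5 is 82 − 1 = 81 days after, or 11 × 7 + 4.

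**5. What cannot be computed.** The documents give no QTc standard deviation and no effect of session position on QTc. No figure in milliseconds follows, and no sign.

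**The case against.** The case for leaving the plan alone has real force.

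- **Only descriptive.** SAP 8.1 applies no inference to safety variables unless otherwise specified. There are about 15 patients, ECGs are done only at equipped sites (Protocol Table 1 footnote), and no decision rule uses the Week 12 pre-dose change. In a single arm that change cannot be attributed to SNF472 anyway. This limits the weight of the point. It does not remove it: confounding with time is unavoidable here, whereas this component comes from the schedule and is not.
- **The within-visit contrast fits the stated mechanism better.** The protocol describes the QT risk as linked to peak concentration through calcium chelation, and SAP 9.4.2 expects no accumulation. Pre-dose to end-of-infusion change uses a same-session reference. This stands, and it is wrong to say that nothing in the plan escapes the mismatch. But that contrast addresses the acute effect over one dialysis session and infusion, not a sustained change.
- **The 3-day gap before baseline is inferred.** Correct. Step 3 shows the mismatch can reverse or vanish for individual patients. The planned comparison is therefore uncontrolled, not biased in a known direction.
- **The data may already be in hand.** Parts of the SAP use the past tense, so rescheduling may be moot. The fix allows for that.

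A reader might also infer that the electrolyte summaries share the fault, since SAP 9.3.2 says "the differences in absolute change from Baseline to all measures will be summarized". The documents do not support this. That section gives weeks without days for K/Mg/iron/zinc and for ionised calcium, and the damaged table columns cannot settle the Week 12 day.

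**Conclusion.** The point holds for the ECG. The Week 1 to Week 12 pre-dose QTc change, and the pre-dose shift table to Week 12, compare readings from different positions in the dialysis week: nominally a 3-day gap at baseline and a 2-day gap at Week 12. Week 1 to Week 6 is matched. This rests on the 1/3/5 grid and on a stable dialysis routine that includes the sessions before study start. The protocol's own list of QTc causes makes the difference relevant. It is an inexpensive improvement to a safety summary; it touches no efficacy result.

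Three stronger readings should be resisted.

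- **A size of bias.** Assuming 4-hour sessions, one could write 72 − 4 = 68 h against 48 − 4 = 44 h, and 1 − 44/68 = 35% less build-up of a solute at Week 12. That is a share of an assumed linear accumulation. It is not a QTc shift, and the protocol does not say that Ca, Mg and K build up between sessions.
- **Week 12 as the only long-exposure comparison.** Week 6 pre-dose ECGs are planned and matched, and QTc thresholds are also counted at any time after the first infusion.
- **An electrolyte bias.** Not established, for the reason given in the objection.

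**What to change.** **If the schedule can still change:** take the Week 12 pre-dose and end-of-infusion ECG at Week 12 Day 1, and align Protocol Table 1 and SAP 9.3.3. That session is already a dialysis visit, so no visit or ECG is added. By step 4 of the working it matches baseline whichever session the patient started on. The cost is small: Day 1 of Week 12 is session 11 × 3 + 1 = 34 of 36, so the last on-treatment ECG precedes the final two infusions.

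**If the data are already collected:**

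- Present Week 6 Day 1 against Week 1 Day 1 as the matched pre-dose ECG contrast.
- Keep the Week 12 Day 5 pre-dose change and shift table, labelled as taken at a different session position from baseline.
- List time since last dialysis at each pre-dose ECG where recorded. SAP 9.1.7 already uses dialysis start and end times, though the session before Week 1 Day 1 may not have been captured.

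**Scope.** This is for the ECG only. For K/Mg/iron/zinc and ionised calcium, SAP 9.3.2 should simply state the Week 12 sampling day. The Week 6 fallback cannot be used for the pre- and post-dose K/Mg/iron/zinc series, which has no Week 6 sample.

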8.8 Baseline values

Baseline is considered the value collected at the Day 1 Week 1 visit. If Day 1 Week 1 value is missing, the Screening value will be used as baseline. If neither a Day 1 Week 1 or Screening value

is available, then the baseline value will be imputed according to the MI and LOCF methods described in Section 8.4.

Some analyses will be also presented comparing pre-dose and post-dose effects. Unless otherwise specified, post-dose and pre-dose comparisons will be done using data from the same study day.

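### SAP 9.3.3 counts QTc increases from an unnamed pre-dose value, and the same-day default does not match the protocol's from-baseline rule

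*SAP*

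**What the plan says.** Protocol 7.1.4, under Electrocardiogram Abnormalities, has a two-part rule. QTcB above 500 ms is abnormal, and so is an "increase >60 ms from baseline in 1 or more subjects as confirmed with consecutive ECGs will be considered abnormal".

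SAP 9.3.3 counts subjects above 450, 480 and 500 ms, the last as "number of subjects with QTc interval > 500 ms". It then counts subjects whose increase from pre-dose exceeds 30 or 60 ms, the latter as "number of subjects with QTc interval increases from predose > 60 ms". Both sets are for QTcB and QTcF. The counts are made once over all ECGs after the first infusion, and again "summarized by visits Week 1 day 1, Week 6 day 1 and Week 12 day 5 for pre-dose and post-dose time-points".

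SAP 8.8 supplies two definitions. For baseline: "Baseline is considered the value collected at the Day 1 Week 1 visit", with Screening as the fallback. For pre/post comparisons: "Unless otherwise specified, post-dose and pre-dose comparisons will be done using data from the same study day".

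SAP 9.3.3 also summarises QTc change as a continuous measure in two ways: pre-dose to post-dose within a visit, and Week 1 Day 1 pre-dose to later pre-dose ECGs. The shift tables of the clinical ECG assessment follow the same split.

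**The concern.** No increase count in the SAP is tied to baseline, although the protocol's increase rule is. If pre-dose means same-day, each count at Weeks 6 and 12 removes whatever change has built up since Week 1. End-of-infusion QTc at those visits, where a rise between visits and a rise during infusion add together, is then not summarised against baseline at all. The Follow-up ECG gets no change count either.

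This matters because the trial has a single arm, so each patient's own baseline is the only comparator. Treatment lasts 12 weeks, against up to 28 days in the earlier haemodialysis studies described in Protocol 2.3. Protocol 7.1.4 itself lists causes of prolongation that can change between visits, such as electrolytes, calcimimetics and sodium thiosulfate.

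**Working it through.** **Decomposition.** Let B be QTc at Week 1 Day 1 pre-dose, P the pre-dose value at a later visit and E the end-of-infusion value at that visit. Then

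E − B = (P − B) + (E − P).

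The protocol rule looks at E − B. A same-day count looks at E − P only. The SAP's continuous summary from Week 1 looks at P − B only. On the same-day reading the sum is not tabulated.

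**What each reference gives at each ECG.**

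| ECG | Same-day pre-dose reference | Week 1 Day 1 pre-dose reference |
|---|---|---|
| Week 1 end of infusion | E − B | E − B (identical) |
| Week 6 and 12 pre-dose | zero by construction | P − B |
| Week 6 and 12 end of infusion | E − P | E − B |
| Follow-up | no same-day pre-dose ECG | Follow-up value − B |

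SAP 9.3.3 asks for the counts at pre-dose time-points and anywhere after the first infusion. Rows 2 and 4 therefore do not fit a same-day reference, while SAP 8.8 points to one. The text does not settle the question.

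**Example.** P − B = 35 ms and E − P = 30 ms give E − B = 65 ms. That exceeds 60 ms from baseline. The same-day increase is 30 ms, which is not above 30, so neither increase count includes it. The absolute counts pick it up only if B is high enough: B > 450 − 65 = 385 ms for the 450 ms count, B > 415 ms for 480 ms, and B > 435 ms for 500 ms.

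**How large the gap could be.** The documents give no QTc variability, infusion effect or drift, and no figure to reproduce, so this is an illustration on assumed inputs. The model is QTc = subject mean + day effect + drift + infusion shift (end-of-infusion ECGs only) + within-day error.

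- Subject mean: 450 ms, SD 25.
- Between-day SD: 10, 20 or 30 ms.
- Within-day SD: 10 or 20 ms.
- Infusion shift: 0, 20, 40 or 60 ms.
- Drift: 0 or 20 ms by Week 12, half of it at Week 6.
- ECGs: pre and post at Weeks 1, 6 and 12, plus Follow-up.
- 3 × 2 × 4 × 2 = 48 settings, 400,000 simulated subjects each. Confirmation by consecutive ECGs is not modelled.

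On the same-day reading:

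| Infusion shift (ms) | A: of subjects >60 ms above baseline, missed by same-day >60 count | B: as A, and also never >500 ms | C: of subjects meeting either part of the rule, caught by neither the same-day >60 nor the >500 count |
|---|---|---|---|
| 0 | 78–100% | 28–71% | 4–26% |
| 20 | 48–99% | 17–54% | 8–21% |
| 40 | 21–74% | 6–22% | 4–13% |
| 60 | 5–10% | 1–2% | 1% |

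B uses the same denominator as A. C is lower than B because its denominator also includes subjects who meet the rule only through the 500 ms limit. If pre-dose means Week 1 Day 1 pre-dose, the loss due to the reference is zero throughout.

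**The case against.** The strongest reply is that the same-day reading is an inference. SAP 8.8 governs pre/post comparisons and yields where something else is specified. SAP 9.3.3 mentions the Week 1 Day 1 pre-dose ECG shortly before the counts, and only that reference makes every requested cell usable. The counts point to table shells that were not in the text available here and might name the reference. This stands as a reason not to call the reference settled. It does not remove the point, because a reference that has to be guessed needs the same edit. The wording also leans the other way. Where 9.3.3 means Week 1 it says so, and SAP 9.3.2 compares electrolytes with baseline at all measurements while the ECG text stops at later pre-dose ECGs.

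It is also fair to say that little is lost outright. The 500 ms limit is counted, the two references coincide at Week 1, and SAP 8.1 provides for listings of all data. A finding that the investigator judges clinically relevant becomes an adverse event and enters those tables. The SAP presents its counts as ICH E14 analyses, not as an implementation of the protocol rule, and it does not carry over the confirmation by consecutive ECGs. With about 15 patients, and ECGs only at equipped sites, cases can be read from listings. All of this stands, and it limits the weakness to the summary tables.

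A reader might go further and infer that most events meeting the protocol rule would go untabulated. A calculation restricted to a later end-of-infusion ECG, with a mean infusion change of 0 to 20 ms, does give 77% to nearly 100%. But those inputs are assumed, and the calculation leaves out the 500 ms limit and Week 1. Column C stays below half in every setting, so the documents do not support that inference.

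**Conclusion.** The mismatch is real and worth correcting. The SAP's increase counts do not name their reference. The default in SAP 8.8 differs from the protocol's from-baseline rule and conflicts with the time-points that SAP 9.3.3 itself requests. On the same-day reading, a rise built up between visits, or across visits plus infusion, can exceed 60 ms from baseline and appear in no increase count. It would then be visible in listings, in the absolute-value counts if it crosses 450, 480 or 500 ms, or as an adverse event if reported as one.

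The share affected cannot be determined from the documents. Over the assumed range it is about 5% to 100% of subjects exceeding 60 ms from baseline, and 1% to 26% of subjects meeting the full rule once the 500 ms count is taken into account. If the intended reference is Week 1 Day 1 pre-dose, nothing is missed for this reason and only the wording needs repair.

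**What to change.** In SAP 9.3.3, state the reference for the increase counts. Count QTcB and QTcF increases above 30 and above 60 ms from the Week 1 Day 1 pre-dose ECG at every later pre-dose, end-of-infusion and Follow-up ECG, overall and by visit. Saying pre-dose matters because Week 1 Day 1 has two ECGs and SAP 8.8 does not say which is baseline. Keep the same-day pre/post counts as a separate table, labelled as such. The protocol and SAP wording should then be reconciled.

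The cost is a few extra table rows. The ECGs are already scheduled, and no new data or visits are needed.
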